## 5.5 Pharmacokinetic, Pharmacodynamic, Pharmacogenomic, and Other Biomarker Analyses

Not Applicable

## 5.6 Safety Analyses

The SAS will be used to summarize all safety variables. Safety data will be summarized using descriptive statistics (e.g., n, mean, standard deviation, median, minimum, maximum for continuous variables; and n [percentage] for categorical variables).

Safety variables include treatment-emergent adverse events (TEAEs), vital signs, EpiTrack, BDI-II, PSQI, QOLIE-31, and C-SSRS scores. Study Day 1 for all safety analyses is defined as the date of the first dose of study drug.

### 5.6.1 Extent of Exposure

The extent of exposure to the study drug during the Titration Period and the Maintenance Period will be summarized descriptively. The duration of treatment (Titration Period and Maintenance Period) will be calculated as the number of days between the date the subject receives their first treatment dose and the date the subject receives the last dose of treatment. These values will be used to summarize the extent of exposure to study drug.

The mean daily dose, maximum dose, last dose, and modal dose (mg) for each subject over the Titration period and Maintenance period will be summarized. The mean daily dose will be calculated by taking the average of all the doses taken during the time period weighted by the number of days on each dose, rounded to 1 decimal place (i.e., sum of [days on each dose\*dose]/during the time period).

### 5.6.2 Adverse Events

The AE verbatim descriptions (investigator terms from the eCRF) will be classified into standardized medical terminology using the Medical Dictionary for Regulatory Activities (MedDRA). AEs will be coded to the MedDRA (most recent version) lower level term closest to the verbatim term. The linked MedDRA preferred term (PT) and primary system organ class (SOC) are also captured in the database.

A treatment-emergent AE (TEAE) is defined as an AE that emerged during treatment, having been absent at pretreatment (Baseline) or

- Reemerged during treatment, having been present at pretreatment (Baseline) but stopped before treatment, or
- Worsened in severity during treatment relative to the pretreatment state, when the AE was continuous.

Only those AEs that are treatment emergent will be included in summary tables. All AEs, treatment emergent or otherwise, will be presented in subject data listings.

The TEAEs will be summarized using the Safety Analysis Set. The incidence of TEAEs will be reported as the number (percentage) of subjects with TEAEs by SOC and PT. A subject will be counted only once within an SOC and PT, even if the subject experienced more than 1 TEAE within a specific SOC and PT. The number (percentage) of subjects with TEAEs will also be summarized by maximum severity (mild, moderate, or severe).

The number (percentage) of subjects with TEAEs will also be summarized by relationship to study drug (Yes [related] and No [not related]).

The number (percentage) of subjects with TEAEs leading to death will be summarized by MedDRA SOC, and PT. A patient data listing of all TEAEs leading to death will be provided.

The number (percentage) of subjects with treatment-emergent SAEs will be summarized by MedDRA SOC, and PT. A patient data listing of all SAEs will be provided.

The number (percentage) of subjects with TEAEs leading to discontinuation from study drug will be summarized by MedDRA SOC and PT. A subject data listing of all AEs leading to discontinuation from study drug will be provided.

### 5.6.3 Vital Signs

Descriptive statistics for vital signs parameters (i.e., systolic and diastolic BP, pulse, respiratory rate, temperature, weight) and changes from baseline will be presented by visit.

The number (percentage) of subjects with clinically notable results over all scheduled and unscheduled visits will be summarized using Table 1 below:

**Table 1: Criteria for Clinically Notablea Vital Signs**

Variable	Criterion Value	Change Relative to Baseline
Systolic BP	> 180 mmHg	Increase of $\geq 20$ mmHg
	< 90 mmHg	Decrease of $\geq 20$ mmHg
Diastolic BP	>105 mmHg	Increase of $\geq 15$ mmHg
	< 50 mmHg	Decrease of $\geq 15$ mmHg
Heart Rate	>120 bpm	Increase of $\geq 15$ bpm
	< 50 bpm	Decrease of $\geq 15$ bpm
Weight		Increase of > 7%
		Decrease of > 7%
a: Clinically notable means that a value must have met both the criterion value and satisfied the magnitude of change relative to baseline.		

The number of subjects with abnormal results for blood pressure and heart rate will be summarized using the criteria in Table 2 below.

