### 9.3.1 Inclusion Criteria

Subjects must meet all of the following criteria to be included in this study:

1. Subjects will be male or female and no younger than 4 years of age and be able to swallow perampanel tablets. (revised per Amendment 01)
2. Subjects must have a diagnosis of epilepsy with POS with or without SGS, or with PGTCS. Either of the following must have occurred to support an epilepsy diagnosis: (revised per Amendment 01)
  - a. At least 2 unprovoked (or reflex) seizures occurring greater than 24 hours apart

- b. 1 unprovoked (or reflex) seizure with EEG evidence of seizures
3. Subjects who receive perampanel as a 1st adjunctive therapy must currently have been treated with stable doses of monotherapy with an AED for 8 weeks prior to Visit 2 (Week 0), have not previously received adjunctive AED treatment, and must, in the investigator's judgement, be in need of initial adjunctive therapy after failure to control seizures with AED monotherapy, at the optimal dose and duration. (revised per Amendment 01)
4. Subjects who receive perampanel as monotherapy, who were newly diagnosed (treatment naïve), following the defined diagnosis of epilepsy. (revised per Amendment 01)
5. Subjects who are currently receiving monotherapy treatment may receive perampanel as monotherapy if, in the investigator's judgment, the subject may benefit from a change in monotherapy treatment. Subjects must not have previously received adjunctive AED treatment.
6. If antidepressants or antianxiety drugs are used, subjects must be on a stable dose regimen of these drugs during the 8 weeks before Visit 2 (Week 0).

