#### **9.5.1.1.4      MEDICAL HISTORY**

Medical and surgical history and current medical conditions will be recorded at the Screening Visit. All pertinent medical and surgical history within 5 years before the Screening Visit must be noted on the appropriate eCRF.

Vital signs including blood pressure, body temperature, respiratory rate and pulse rate will be performed as designated in [Section 9.5.1.6.4](#). Documentation of vital signs will be included in the source documentation at the site. Weight should be recorded at each visit, and height should be recorded at baseline. For subjects <18 years of age, height should also be recorded at the last Follow-Up Visit.

Prior and concomitant medications including drug name, dosage, administration route, within 24 weeks (and as long as available, for AEDs) before the Screening Visit will be recorded.

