### 3.2 Overall Study Design and Plan

This is a multi-center, open-label, Phase 4 study. Subjects who met all of the inclusion and none of the exclusion criteria will receive perampanel. Baseline seizure counts (frequency) data will be collected by subjects or guardian/legally authorized representative, retrospectively (for history prior to screening) and prospectively as needed (during baseline). The study consists of 4 periods: a Screening Period (to start no earlier than 6 weeks before the 1st dose of study drug), a Titration Period (13 weeks), a Maintenance Period (39 weeks), and a Follow-up Period (4 weeks). The study duration for each subject is expected to be approximately 1 year in total.

Study subjects includes the following:

- Subjects who have been diagnosed with POS or PGTCS but have not previously received treatment with an antiepileptic drug (AED) or are receiving monotherapy treatment (no history of AED polytherapy) and wish to switch to another monotherapy treatment; or
- Subjects who are receiving treatment with a single AED administered at a stable dose for at least 8 weeks before Visit 2 (Week 0) and needs additional AED treatment; subjects should not have previously received adjunctive AED therapy.

An overview of the study design is presented below.

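### The single 7% weight-change flag in SAP 5.6.3 takes no account of growth, so in children it can count normal growth as notable gain and miss a failure to gain

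*SAP*

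**What the plan says.** SAP 5.6.3, Table 1, has two weight rows: "Increase of > 7" percent and "Decrease of > 7" percent, both relative to baseline. The criterion-value cell for weight is empty, and no age, sex, height or growth reference is given. Footnote a says that "a value must have met both the criterion value and satisfied the magnitude of change relative to baseline".

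The count is cumulative over the study: "The number (percentage) of subjects with clinically notable results over all scheduled and unscheduled visits will be summarized using Table 1 below". Under SAP 8.2.1 the baseline is the last pre-dose value, so it stays fixed for the year.

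Protocol 9.3.1 admits subjects "no younger than 4 years of age and be able to swallow perampanel tablets", with no upper age limit. SAP 3.2 gives "a Titration Period (13 weeks), a Maintenance Period (39 weeks" weeks), 52 weeks in all. SAP 5.4 notes that there is no control arm.

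SAP 5.3.4 produces safety summaries by seizure type and overall. Its age groups (<12, 12-<=18, 18-<=65, >65) apply only to retention and the seizure endpoints.

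Protocol 9.5.1.1.4 has weight recorded at each visit and height at baseline, and adds: "For subjects <18 years of age, height should also be recorded at the last Follow-Up Visit". Height is not among the vital-sign parameters in SAP 5.6.3.

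**The concern.** A percentage change from a fixed baseline means different things in an adult, whose expected change over a year is near zero, and in a child, whose expected change is a gain. Applied to both, the flag mixes a possible drug effect with growth. With no control arm and no age split, the reader cannot separate the two.

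The error runs in both directions. The increase flag can fire with no drug effect. The decrease flag asks for a real loss of more than 7%, so a child whose weight stands still all year is recorded as unremarkable.

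What is at stake is the reading of one descriptive safety table. Weight is, however, a named safety assessment in Protocol 9.5.1.6. The SAP also adjusts for age elsewhere: its section 13.1 corrects EpiTrack totals by age. SAP section 7 reports that enrolment stopped early and that confidence intervals will not be calculated, so each growth-related flag would move a bare percentage on a small denominator.

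**Working it through.** The plan states no expected flag rate, so there is no figure of its own to reproduce.

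**Inputs from the documents:** cut-off 7% (SAP 5.6.3, Table 1); treatment 13 + 39 = 52 weeks (SAP 3.2); vital signs after baseline at Weeks 13, 26, 39 and 52 (Protocol Table 4).

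**Assumptions, not in the documents:** annual weight gain of 1 to 3 kg, accruing linearly; baseline weights of 16 to 40 kg; the share of children enrolled; the share of those children who are flagged.

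**Step 1: size of the trigger and time to reach it.** Trigger in kg = 0.07 × baseline weight. Week of crossing = 52 × trigger / annual gain.

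| Baseline | Trigger | Assumed gain per year | Gain at 52 weeks | Week 7% is crossed |
|---|---|---|---|---|
| 16 kg | 1.12 kg | 1 kg | 1/16 = 6.25% | 58.2 (not reached) |
| 16 kg | 1.12 kg | 2 kg | 2/16 = 12.5% | 29.1 |
| 20 kg | 1.40 kg | 2 kg | 2/20 = 10.0% | 36.4 |
| 25 kg | 1.75 kg | 1.5 kg | 1.5/25 = 6.0% | 60.7 (not reached) |
| 25 kg | 1.75 kg | 2 kg | 2/25 = 8.0% | 45.5 |
| 40 kg | 2.80 kg | 2 kg | 2/40 = 5.0% | 72.8 (not reached) |
| 40 kg | 2.80 kg | 3 kg | 3/40 = 7.5% | 48.5 |

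The flag can be recorded only when weight is measured. At 2 kg a year, the 16 kg child is first caught on schedule at Week 39 and the 25 kg child at Week 52, unless an unscheduled visit comes sooner. A child who leaves before crossing is not counted.

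**Step 2: the decrease flag.** Take a 20 kg child expected to reach 22 kg at the assumed 2 kg a year. With no gain at all, the change is 0% and nothing is flagged. To be flagged, weight must fall below 20 − 1.40 = 18.6 kg. That is 22 − 18.6 = 3.4 kg under the expected weight, or 3.4/22 = 15.5%.

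**Step 3: contribution to the pooled percentage.** Points contributed = share of children × share of children flagged through growth.

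| Assumed share of children | 50% of them flagged | 95% of them flagged |
|---|---|---|
| 5% | 2.5 points | 4.75 points |
| 20% | 10 points | 19 points |

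With no children enrolled, the contribution is zero.

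**The case against.** The best defence is that the effect may be very small. The documents give neither growth rates nor the number of children. Enrolment stopped short, tablets must be swallowed whole, and the secondary safety endpoint in SAP 5.1.2 names adolescents and adults. The table is descriptive, and retention and seizure results do not depend on it. All of this stands, and it is why the point is minor. It does not remove the fault in the rule. The by-visit change in weight in SAP 5.6.3 does not make up for it either, because that summary is also pooled over age.

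Three stronger readings are tempting, and the documents do not support them.

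- A reader might infer that every child below some weight is flagged by growth. Any such limit comes from an assumed growth rate: 1.5/0.07 = 21.4 kg at 1.5 kg a year, 3/0.07 = 42.9 kg at 3 kg a year. These are two different cut-offs, and early discontinuation lowers the count further.
- A reader might infer from footnote a that no weight can ever qualify, since weight has no criterion value. A blank criterion beside a filled change cell is more naturally read as change only. The footnote needs a clarification and no more.
- A reader might extend the point to the blood-pressure and heart-rate limits, which also serve all ages. The documents give no paediatric figures against which to judge them. The value-and-change rule also restrains them: a child whose systolic pressure is usually below 90 mmHg is flagged in Table 1 only after a fall of at least 20 mmHg.

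**Conclusion.** The concern holds as a minor one. As written, the rule applies one fixed 7% change to subjects from age 4 for up to 52 weeks, pooled over age and without a control. Many growing children could be counted as having notable gain through growth alone, and a child who fails to gain is not picked up.

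The direction of the fault follows from the documents. Its size does not. Growth at 2 kg a year flags children of 16 to 25 kg by about weeks 29 to 46, but slower growth or early withdrawal may flag none. The pooled effect runs from zero with no children to 19 points at an assumed 20% share with 95% flagged. A reader might go on to infer that the table would be taken as evidence of a drug effect on weight. The plan makes no such claim, and the most that can be said is that the table could not tell growth from such an effect.

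**What to change.** In SAP 5.6.3:

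1. Present the clinically notable weight table by the age groups already defined in SAP 5.3.4. As written, age 18 falls in both 12-<=18 and 18-<=65, so assign it to one group first.
2. State that the fixed 7% flag is to be interpreted in adults only.
3. For subjects under 18, summarise change from baseline in age- and sex-standardised weight against a growth reference named in the SAP. If few are enrolled, list them individually instead. Height is scheduled only at baseline and the last Follow-Up Visit, so a weight-for-age score is the one available throughout.
4. Add to footnote a that weight is judged on change alone.

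This is a cheap improvement. Weight, sex and date of birth or age are already collected (Protocol 9.5.1.1.1 and 9.5.1.1.4), so no new data are needed. The cost is one extra derivation, a split table and small paediatric counts. If a site recorded age rather than date of birth, the standardised score will be coarser.

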**Table 2: Criteria for Abnormal Vital Signs**

Variable	Change Relative to Baseline
Systolic BP	Increase of $\geq 20$ mmHg
	Decrease of $\geq 20$ mmHg
	Increase of $\geq 40$ mmHg
	Decrease of $\geq 40$ mmHg
Diastolic BP	Increase of $\geq 10$ mmHg
	Decrease of $\geq 10$ mmHg
	Increase of $\geq 20$ mmHg
	Decrease of $\geq 20$ mmHg
Pulse	Increase of $\geq 15$ bpm
	Decrease of $\geq 15$ bpm
	Increase of $\geq 30$ bpm
	Decrease of $\geq 30$ bpm

#### 5.6.4 Other Safety Analyses

##### **EpiTrack**

Cognition will be assessed in subjects 6 years of age and older at Visit 2 (Week 0) and at 3 and 12-month visits (Visits 4 and 7, respectively) using the EpiTrack® assessment tools (EpiTrack for subjects aged 16 years and older and EpiTrack Junior for subjects aged 6 to 16 years at Visit 2 [Week 0]?). The EpiTrack includes 6 subtests: response inhibition, visuo-motor speed, mental flexibility, visual motor planning, verbal fluency, and working memory. Based on the subtest results, an age-corrected total score is calculated. “Higher total scores indicate more severe depressive symptoms. The calculation details and performance categories are provided in Section 13.1. Practice corrected reliable change indices indicate a significant change with a gain of more than 3 points and a loss of more than 2 points.

Descriptive statistics for age-corrected total score and changes from baseline will be presented by visit. Summaries of the proportion of subjects with no/mild/clear cognitive impairment and shifts between these categories from baseline to end of treatment will be produced.

##### **Beck Depression Inventory-II (BDI-II)**

The Beck Depression Inventory-II (BDI-II) is a 21-question multiple-choice self-report inventory and is widely used for measuring the severity of depression. The BDI-II will be administered in subjects 16 years of age and older who are administered the EpiTrack.

There is a four-point scale for each item ranging from 0 to 3. Each of the 21 items corresponding to a symptom of depression is summed to give a single total score for the BDI-II from 0 to 63. Higher total scores indicate more severe depressive symptoms. Descriptive statistics for BDI-II total score and changes from baseline will be presented by visit.

### **Pittsburgh Sleep Quality Index (PSQI)**

Based on 19 items, the PSQI measures several different aspects of sleep, offering seven component scores and one composite score. The component scores consist of subjective sleep quality, sleep latency (i.e., how long it takes to fall asleep), sleep duration, habitual sleep efficiency (i.e., the percentage of time in bed that one is asleep), sleep disturbances, use of sleeping medication, and daytime dysfunction.

Each item is weighted on a 0–3 interval scale. The global PSQI score is then calculated by totaling the seven component scores, providing an overall score ranging from 0 to 21, where lower scores denote a healthier sleep quality. The scoring details of global PSQI score are provided by PSQI website: <http://www.psychiatry.pitt.edu/node/8240>. Descriptive statistics for individual component and global PSQI scores and changes from baseline will be presented by visit.

### **Quality of Life in Epilepsy Inventory-31 (QOLIE-31)**

The QOLIE-31 contains 7 multi-item scales that tap the following health concepts: emotional well-being, social functioning, energy/fatigue, cognitive functioning, seizure worry, medication effects, and overall quality of life. A QOLIE-31 overall score is obtained using a weighted average of the multi-item scale scores. Scoring details of the QOLIE-31 overall score will be performed as instructed by RAND QOLIE-31 scoring manual website: [https://www.rand.org/content/dam/rand/www/external/health/surveys\\_tools/qolie/qolie31\\_scoring.pdf](https://www.rand.org/content/dam/rand/www/external/health/surveys_tools/qolie/qolie31_scoring.pdf). The QOLIE-31 also includes a single item that assesses overall health. QOLIE-31 raw scores are scaled from 0-100 with higher scores reflecting better quality of life. The overall score is calculated by summing the scale scores after weighting with empirically derived weights provided in the manual. Descriptive statistics for QOLIE-31 subscale and overall score and changes from baseline will be presented by visit.

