### 5.1.3 Exploratory Endpoints

- 50% responder rate in total POS, SGS, and PGTCs; 50% responders are defined as subjects who have at least a 50% reduction in seizure frequency relative to baseline (in subjects with sufficient baseline seizure frequency data).
- 75% responder rate in total POS, SGS, and PGTCs; 75% responders are defined as subjects who have at least a 75% reduction in seizure frequency relative to baseline (in subjects with sufficient baseline seizure frequency data)
- Median percent change in total POS, SGS, and PGTCs frequency in the Titration and Maintenance Periods relative to baseline (in subjects with sufficient baseline seizure frequency data)
- Proportion of subjects with no/mild/clear cognitive impairment relative to baseline using the EpiTrack total score
- Change in subjective sleep quality at the end of the Maintenance Period relative to baseline using the PSQI
- Change in quality of life at the end of the Maintenance Period relative to baseline using the QOLIE-31
- Proportion of subjects with Depression relative to baseline using BDI-II scores.

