#### 5.3.5.2 Safety

The algorithm on the assumptions used for imputing the missing dates for AEs is given in the programming specifications.

If the day and month are missing, events will be considered treatment-emergent if the year is equal to or after the year of the first dose date; if days are missing, events will be considered treatment-emergent if the year is after the year of the first dose, or if the year is equal to the year of the first dose date and the month is equal to or after the month of the first dose date.

For the purpose of summarizing maximum severity, if the severity of an adverse event (AE) is missing for a subject, then, if this subject has another AE with the same preferred term that has “severe” severity, the maximum severity of the AE will be noted as “severe”; otherwise the maximum severity will be noted as missing. Similarly, for the purpose of summarizing closest relationship, if the relationship of an AE to study drug is missing, the AE will be noted to be related if there is another related AE with the same preferred term, otherwise this relationship will be noted as missing.

The algorithm to impute missing dates for concomitant medications is given in the programming specifications. No special handling of missing data is planned for the analysis of any other safety variables.

Data exceptions or outliers will be determined by inspection of the tables, listings, and graphs in consultation with the clinical study team. The effect of outliers on analyses may be assessed by re-analyzing the data without the outliers.

All the listings will display the original missing values.

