### 8.2.2 Treatment Duration for Safety Analyses

For AEs, the treatment duration is considered to begin on Day 1 and ends 28 days after the last dose of treatment.

For summaries of safety by time points, the time points will be relative to date of first dose. For standardized reporting, study day windows relative to the first dose (Day 1) in the study will be applied to determine into which study week the data will be mapped. Scheduled, unscheduled, and early withdrawal visits will be mapped into study weeks. Table 1 below gives the mapping of relative day ranges to week for non-AE safety variables. If a subject did not have a recorded observation falling within a given range of days in order to be assigned to a study week, the subject's data for that week will be regarded as missing for summarization purposes. If there are two or more assessments in the same window then:

- if the window is the baseline assessment, then the latest assessment will be used in the summary tables.
- if the window is not the baseline assessment, then the assessment closest to the scheduled assessment will be used in the summary tables.

Note that if two assessments are equidistant from the scheduled assessment then the last assessment of the two (within the allowable window) will be used.

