**Table 1: Mapping of Study Day Ranges to Week**

Period	Study Week	Study Day Range (Relative to First Dose of Study Drug)	Target Day
Screening	Baseline	Day $\leq 1^a$	1
Titration	Week 13	$2 \leq \text{Day} \leq 138$	92
Maintenance	Week 26	$139 \leq \text{Day} \leq 229$	183
Maintenance	Week 39	$230 \leq \text{Day} \leq 320$	274
Maintenance	Week 52	$321 \leq \text{Day} \leq 999^b$	365

- a: All assessments at Visit 2 were to be performed prior to first dose of study drug; results from these assessments will be regarded as Pretreatment values in the analyses.
- b: The last non-missing value measured in the treatment duration will be handled as the data of EOT of the Study. The Follow-up visit will not be included in this analysis visit.

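### QOLIE-31 and PSQI change is planned only by visit, so the Week 52 row is almost wholly completers, and no end-of-treatment result is named for early leavers

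*SAP*

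**What the plan says.** **Endpoints.** SAP 5.1.3 lists two exploratory endpoints: "Change in quality of life at the end of the Maintenance Period relative to baseline using the QOLIE-31" and "Change in subjective sleep quality at the end of the Maintenance Period relative to baseline using the PSQI". The protocol synopsis and Protocol 9.7.1.1.3 define them the same way.

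**Collection.** Protocol Table 4 marks both scales at Week 0, Week 52 and Early Discontinuation, and nowhere else. Protocol 9.5.5 requires everyone who leaves early to complete the Early Discontinuation procedures.

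**Planned summaries.** SAP 5.6 classes both scales as safety variables: "Safety variables include treatment-emergent adverse events (TEAEs), vital signs, EpiTrack, BDI-II, PSQI, QOLIE-31, and C-SSRS scores". SAP 5.6.4 then gives one analysis sentence for each: "Descriptive statistics for QOLIE-31 subscale and overall score and changes from baseline will be presented by visit" and "Descriptive statistics for individual component and global PSQI scores and changes from baseline will be presented by visit".

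**Rules for missing and early values.**
- SAP 5.3.5.2, after its rules for AEs and medication dates: "No special handling of missing data is planned for the analysis of any other safety variables".
- SAP 8.2.2 places early-withdrawal assessments, like all others, in a study week according to study day. If nothing falls in a window, "the subject's data for that week will be regarded as missing for summarization purposes".
- Note b to the Week 52 row of the mapping table: "The last non-missing value measured in the treatment duration will be handled as the data of EOT of the Study". SAP 8.1.2 has a similar on-treatment definition of EOT.
- SAP 8.2.3 says that, for a list of datasets including PSQI and QOLIE-31, the record labelled as the scheduled visit is the one analysed.

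**The concern.** Each subject has at most one planned post-baseline value on these scales: Week 52 for those who stay, the exit visit for those who leave. Sorting those values by visit therefore sorts subjects by whether they stayed. The row that matches the endpoint, Week 52, describes the stayers. The protocol's own rationale (9.2.2) treats staying on drug as a sign that efficacy and safety are satisfactory, and adverse events and lack of efficacy are among its listed withdrawal reasons (9.3.3.2). QOLIE-31 includes subscales on seizure worry and medication effects, so some reasons for leaving overlap with what is measured.

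The exploratory objectives concern subjects given perampanel, not only those who remain at one year. There is no control arm against which selection could cancel, so a Week 52 change could be read as an effect of the drug. A reader scanning the by-visit table could also mistake a change in who is being measured for a change over time.

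Elsewhere the SAP does state how dropouts count. Seizure frequency in Maintenance has an LOCF rule (5.3.5.1), and early dropouts are non-achievers for seizure freedom and conversion (5.4.2). For these two endpoints no such choice is stated.

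**Working it through.** The plan gives no figure to reproduce on this point: no SD for either scale and no expected dropout rate.

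**Step 1. Where each value lands (SAP 8.2.2 mapping table against Protocol Table 4).**

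| Row | Study days | QOLIE-31/PSQI scheduled? | Who supplies values |
|---|---|---|---|
| Week 13 | 2 to 138 | No | Early leavers |
| Week 26 | 139 to 229 | No | Early leavers |
| Week 39 | 230 to 320 | No | Early leavers |
| Week 52 | 321 to 999 | Yes | Completers, plus any exits from Day 321 |

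Apart from unscheduled assessments, the first three rows contain discontinuers only.

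**Step 2. Which rule governs exit values.** By 8.2.2 they are used, in the row where they fall. By a literal reading of 8.2.3 they are not scheduled-visit records and are not used. By note b they become the EOT value, but 5.6.4 names no EOT summary for these scales. For EpiTrack, 5.6.4 does ask for category shifts to end of treatment. Two programmers could follow this text and report different sets of subjects.

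**Step 3. Possible size of selection at Week 52.** All inputs are assumptions. Let true mean change be zero, d the share without a Week 52 value, and ρ the correlation between staying and favourable change (normal selection). Positive means favourable, so the sign is reversed for PSQI, where lower is better. Results are in SDs of change.

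Bias at Week 52 = ρ·φ(z_d)/(1−d). With d = 0.30, φ(z_d) = 0.3477, and ρ = 0.3: 0.3 × 0.3477/0.70 = **+0.149**. A simulation gave 0.150.

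| d | 10% | 20% | 30% | 40% | 50% |
|---|---|---|---|---|---|
| ρ = 0.3 | +0.058 | +0.105 | +0.149 | +0.193 | +0.239 |

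At d = 30%: ρ = 0.5 gives +0.248, ρ = 0.2 gives +0.099, ρ = 0 gives 0, and ρ = −0.2 gives −0.099.

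**Step 4. The leavers' rows.** In the same case, the leavers' mean is −ρ·φ(z_d)/d = −0.3 × 0.3477/0.30 = −0.348. If all leavers were assessed, the earlier rows together would average about −0.35 and Week 52 about +0.15. That is an apparent rise of about 0.50 SD with no true change.

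**Step 5. A mechanism with the opposite sign.** If dropout depends only on a poor baseline, completers' bias = (r−1)·a·φ(z_d)/(1−d), in SDs of score. Here a is the correlation of staying with baseline score and r the baseline to Week 52 correlation. At d = 30%, a = 0.3 and r = 0.7 give −0.3 × 0.3 × 0.497 = −0.045; a = 0.5 and r = 0.5 give −0.5 × 0.5 × 0.497 = −0.124.

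**Step 6. What an EOT summary would do.** If a share c of leavers have an exit value, and that value reflects their change, EOT bias = ρ·φ(z_d)·(1−c)/[(1−d)+c·d]. At d = 30%, ρ = 0.3:
- c = 100%: 0
- c = 80%: 0.3 × 0.3477 × 0.2/0.94 = +0.022
- c = 50%: 0.3 × 0.3477 × 0.5/0.85 = +0.061

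**The case against.** Several stronger readings are tempting, and the documents do not support them.

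- **That the SAP has no missing-data handling for these scales.** It plans no special handling, but it has a week mapping that covers early-withdrawal visits and an EOT definition. The gap is that none of this is tied to the end-of-Maintenance result.
- **That early leavers vanish from the tables.** Under 8.2.2 they are absent from the Week 52 row but appear in earlier rows. Only a literal reading of 8.2.3 removes them. Its heading concerns replicate data, so it may be meant only to choose between duplicates, but its text is not limited to that.
- **That the Week 52 change must look favourable.** Steps 3 and 5 show that it can be zero or negative. Protocol 9.3.3.2 and 9.5.5 also list loss to follow-up, withdrawn consent, eligibility violation, pregnancy and sponsor termination, which need not track the scores.
- **That EOT should replace Week 52.** The endpoint is defined at the end of Maintenance, which Protocol 9.3.3.1 places at the Week 52 visit. EOT would include subjects who left during titration, so it belongs beside Week 52.

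The defence can add that table shells and programming specifications are separate documents (SAP 9 and 11) and may contain an EOT row. It can also say that safety summaries show n, that discontinuation reasons are tabulated, and that these are exploratory, descriptive endpoints in a study with no hypothesis and curtailed enrolment. This limits the weight of the point. It does not settle which row is the endpoint, or whether exit values count, and those choices belong in the SAP.

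**Conclusion.** The point holds in a limited form. As written, the by-visit rules make the Week 52 row for QOLIE-31 and PSQI almost wholly completers and the Week 13, 26 and 39 rows almost wholly discontinuers. SAP 8.2.2 and 8.2.3 conflict on whether exit values are used, and EOT is not named as a result for either scale. These conclusions rest on the text alone.

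A favourable Week 52 change with no drug effect is a risk, not a finding. Under the assumed model with ρ = 0.3 it is about +0.06 to +0.24 SD for 10% to 50% loss. It disappears with no correlation and reverses if poor baseline drives dropout. Dropout, correlations and SDs are all absent from the documents. I leave the size in SD units because the scales differ in range and direction (PSQI 0 to 21, lower better; QOLIE-31 0 to 100, higher better), and no single figure in points could serve both. Since the endpoints are exploratory, this is worth correcting but does not touch the primary result.

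**What to change.** In SAP 5.6.4, for QOLIE-31 and PSQI:

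1. Present change from baseline to EOT (last value in the treatment duration, including the Early Discontinuation assessment) beside the Week 52 observed-case change. State explicitly that the exit assessment counts, because the EOT definitions are limited to values on treatment or in the treatment duration and an exit visit may follow the last dose.
2. For subjects without a Week 52 value, give the number, baseline scores and discontinuation reasons.
3. Do not present the Week 13, 26 and 39 rows as a time course for these scales.
4. Reconcile 8.2.3 with 8.2.2 and note b of its mapping table, so that Early Discontinuation values are used.

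The cost is about one extra row per table, a short count of non-assessed subjects and a wording change, all from data the protocol already collects. The small downside is that EOT mixes treatment durations, which is why both rows are shown. The gain also depends on how many leavers complete the exit assessment (step 6 of the working).
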